2.1.3 Tertiary/Exploratory Objectives

- To measure the changes in TAK-659 plasma concentrations when given in combination with ixazomib.
- To quantitatively examine before, and at early timepoint of therapy, the primary mechanistic transcriptional drivers of these AMLs (HOXA and MEIS1), which are postulated to be extinguished by the drug combination, for their ability, when extinguished, to predict subsequent response
- To implicate Syk, Wnt pathway (ID1, JUN, FOXM1, β -catenin) and Wnt antagonists RUNX3 and Cullin 3 and EZH2 in responses affected by combination of TAK-659 and Ixazomib
- To use digital PCR technology to examine the participation of collaborating mutations on depth of remission for the class 1 and class 2 drivers

2.2 Endpoints

2.2.1 Primary Endpoint

Phase I: Maximum tolerated dose (MTD) and recommended Phase II dose (RP2D) for the combination of TAK-659 plus Ixazomib in relapsed or refractory AML

Phase II: Overall response rate (ORR) defined as CR, CRp, CRi, and PR per Revised Recommendations of the International Working Group (IWG) for Diagnosis, Standardization of Response Criteria, Treatment Outcomes, and Reporting Standards for Therapeutic Trials in Acute Myeloid Leukemia.

2.2.2 Secondary Endpoints

- DOR defined as the time from the date of first documentation of a response to the date of first documented progressive disease
- TTP defined as the time from first dose of study drug until tumor progression as defined by the Revised Recommendations of the International Working Group (IWG) for Diagnosis, Standardization of Response Criteria, Treatment Outcomes, and Reporting Standards for Therapeutic Trials in Acute Myeloid Leukemia
- Mortality rate at 3 and 6 months
- OS defined as the time from the date of study entry to death
- ORR, DOR, TTP, mortality rate at 3 and 6 months, and OS in Flt3mutant vs. WT populations

2.2.3 Tertiary/ Exploratory Endpoints

- Changes in TAK-659 plasma concentrations when given in combination with ixazomib.
- Identification of the cytogenetic and next-generation sequencing-derived mutational complement that predicts response to the combination therapy.
- Identification of a gene expression signature which identifies patients prior to therapy whom will achieve remission based on reversal of a pattern for repression of tumor suppressors, esp. RUNX3, and also achieve downregulation of pre-existing overexpressed HOXA and MEIS1, with participation in loss of Wnt pathway agonists (ID1, JUN, FOXM1, β -catenin).

3. ELIGIBILITY CRITERIA

3.1 Inclusion Criteria

Subject must meet all of the following applicable inclusion criteria to participate in this study:

1. Written informed consent and HIPAA authorization for release of personal health information.
NOTE: HIPAA authorization may be included in the informed consent or obtained separately.
2. Male or female patients 18 years or older at the time of consent.
3. Patients must have a diagnosis of primary or secondary AML with relapsed or refractory disease (WHO update 2016, [34]) other than acute promyelocytic leukemia, or complex karyotype or monosomy 7 (or containing monosomy 7) for whom no standard therapies are anticipated to result in a durable remission according to the clinical judgment of the treating physician, or in a patient who refuses standard therapies. However, if the qualifying 3-5 complex karyotypic abnormalities entail recurring translocations/deletions normally of intermediate risk (5q- *or* 7q-, 11q23, MLL-PTD, t(3;21)(q26; q22), CBF+); and/or the mutational profile by NGS has revealed a profile which renders sensitivity to: 1) TAK-659 (DNMT3A; Flt3N676K, Flt3 S451F, in addition to the common Flt3ITD/TKD; combination of ASXL1 plus EZH2; or TET2 or IDH1/2) or to: 2) Ixazomib (NRAS, KRAS, PTPN11/SHP2, PDCD11, WT1), the patient will be eligible.
4. Must have submitted for Next Generation Sequencing (NGS) testing by: 1) (preferred) having submitted a tumor sample for commercial myeloid NGS from Foundation One, Mayo, Tempus, Quest, ARUP or an institutional CLIA-certified laboratory and/or 2) obtaining a bone marrow

aspirate during screening for submission to Foundation One, Mayo, Tempus, Quest, ARUP or an institutional CLIA-certified laboratory and ordered as standard of care. If bone marrow aspiration has failed, a peripheral blood sample with circulating blasts may be substituted. Screening reports on tumor cytogenetics and/or mutation assays (eg, FLT-3, and NGS) performed as part of the standard of care will be recorded in the study database or obtained at the time of screening if not previously available.

5. Patient's disease must be characterized for the presence/absence of Flt3ITD/TKD mutation from an FDA-approved vendor (ex. LabPMM).
6. In addition, patients for the phase 2 portion of the study must meet the following:
 - a. Patients, if relapsed/ refractory, must have exposure to no more than 2 prior chemotherapy regimens. Re-induction with the same regimen or stem cell transplant will not be considered a separate regimen.
 - b. Patients must not have prior exposure to any investigational Flt3 inhibitors (midostaurin or gilteritinib are allowed)
7. Eastern Cooperative Oncology Group (ECOG) performance status 0-2
8. Life expectancy of greater than 3 months as determined by the treating physician.
9. Female patients who:
 - Are postmenopausal for at least 1 year before the screening visit, OR
 - Are surgically sterile, OR
 - If they are of childbearing potential, agree to practice 2 effective methods of contraception at the same time, from the time of signing the informed consent through 180 days after the last dose of study drug, or
 - Agree to practice true abstinence, when this is in line with the preferred and usual lifestyle of the subject. Periodic abstinence [eg, calendar, ovulation, symptothermal, postovulation methods], withdrawal, spermicides only, and lactational amenorrhea are not acceptable methods of contraception. Female and male condoms should not be used together.)
 - Agree not to donate eggs (ova) during the course of this study or 180 days after receiving their last dose of study drug.
10. Male patients, even if surgically sterilized (i.e., status post-vasectomy), who:
 - Agree to practice effective barrier contraception during the entire study treatment period and through 180 days after the last dose of study drug, or
 - Agree to practice true abstinence, when this is in line with the preferred and usual lifestyle of the subject. (Periodic abstinence [eg, calendar, ovulation, symptothermal, postovulation methods for the female partner] and withdrawal are not acceptable methods of contraception. Female and male condoms should not be used together.)
 - Agree not to donate sperm during the course of this study or within 180 days after receiving their last dose of study drug.
11. Voluntary written consent must be given before performance of any study related procedure not part of standard medical care, with the understanding that consent may be withdrawn by the patient at any time without prejudice to future medical care
12. In the absence of rapid progressive disease, the interval from prior systemic anticancer treatment to time of TAK-659/Ixazomib administration should be at least 2 weeks for cytotoxic agents

(other than hydroxyurea), or at least 5 half-lives for noncytotoxic agents, and patients have to have recovered from acute toxicities of these therapies. Patients who are on hydroxyurea may be included in the study and may continue on hydroxyurea for the first 21 days while participating in this study. **NOTE:** For patients with a white blood cell count >50,000/uL, hydroxyurea may be used to control the level of circulating leukemic blast cell counts prior to study entry, and, if needed, concomitantly while on TAK-659 treatment during the first 21 days of the study.

13. Suitable venous access for the study-required blood sampling, and transfusion support.
14. Demonstrate adequate organ function as defined in the table below; all screening labs to be obtained within 28 days prior to registration.

System	Laboratory Value
Renal	
Calculated creatinine clearance	≥ 60 mL/min using the Cockcroft-Gault formula
Pancreas	
Lipase	≤1.5xULN with no clinical symptoms suggestive of
Amylase	pancreatitis or cholecystitis
Hepatic	
Total Bilirubin	≤ 1.5 × upper limit of normal (ULN)
Aspartate aminotransferase (AST)	≤ 2.5 × ULN
Alanine aminotransferase (ALT)	≤ 2.5 × ULN

3.2 Exclusion Criteria

Subjects meeting any of the criteria below may not participate in the study:

1. Clinically active central nervous system leukemia.
2. Female patients who are lactating and breastfeeding (**NOTE:** breast milk cannot be stored for future use while the mother is being treated on study)
3. Female patients who have a positive serum pregnancy test during the screening period or a positive urine pregnancy test on Day 1 before first dose of study drug.
4. Any serious medical or psychiatric illness, including drug or alcohol abuse, that could, in the investigator's opinion, potentially jeopardize the safety of the patient or interfere with the objectives of the study.
5. Prior treatment with investigational agents ≤ 21 days or ≤ 5 half-lives (whichever is shorter) before the first dose of study treatment. A minimum of 10 days should elapse from prior investigational therapy to initiating protocol therapy.
6. Persistent clinically significant toxicity from prior chemotherapy that is Grade 2 or higher by the NCI CTCAE (v5).
7. Receipt of HSCT within 60 days of the first dose of TAK-659/Ixazomib; clinically significant graft-versus-host disease (GVHD) requiring ongoing immunosuppressive therapy post HSCT at the time of screening (use of topical steroids for ongoing skin GVHD is permitted).
8. Active, systemic infection requiring intravenous (IV) antibiotic, antifungal, or antiviral therapy or other serious infection within 10 days before the first dose of study drug.

9. Major surgery within 14 days before the first dose of study drug and have not recovered fully from any complications from surgery.
10. Radiotherapy less than 2 weeks before the first dose of study treatment or have not recovered from acute toxic effects from radiotherapy.
11. Known human immunodeficiency virus (HIV) positive.
12. Known hepatitis B surface antigen positive, or known or suspected active hepatitis C infection (testing not required).
13. Any of the following cardiovascular conditions:
 - Acute myocardial infarction within 6 months before starting study drug.
 - Current or history of New York Heart Association Class III or IV heart failure.
 - Evidence of current, uncontrolled cardiovascular conditions including cardiac arrhythmias, angina, pulmonary hypertension, or electrocardiographic evidence of acute ischemia or active conduction system abnormalities.
 - Fridericia corrected QT interval (QTcF) >450 milliseconds (msec) (men) or >475 msec (women) on a 12-lead ECG during the Screening period.
 - Abnormalities on 12-lead ECG including, but not limited to, changes in rhythm and intervals that, in the opinion of the treating physician, are considered to be clinically significant.
14. Known gastrointestinal (GI) disease or GI procedure that could interfere with the oral absorption or tolerance to study drugs, including difficulty swallowing tablets, diarrhea > Grade I despite supportive therapy.
15. Use or consumption of any of the following medications, supplements, or foods/beverages that are inhibitors or inducers of P-gp or strong reversible inhibitors or inducers of CYP3A within the indicated timeframes below. Note that use or consumption of these substances is not permitted during the study.
 - a) Inhibitors of P-gp and/or strong reversible inhibitors of CYP3A within 5 times the inhibitor half-life (if a reasonable half-life estimate is known), or within 7 days (if a reasonable half-life estimate is unknown), before the first dose of study drug. In general, the use of these agents is not permitted during the study except in cases where an AE must be managed. See Section 5.7.2 and the Documents/Info tab of the electronic data capture (EDC) system for a nonexhaustive list of strong CYP3A reversible inhibitors and/ or Pgp inhibitors based on the FDA Draft DDI Guidance.
 - b) Strong CYP3A mechanism-based inhibitors or strong CYP3A inducers and/or P-gp inducers within 7 days, or within 5 times the inhibitor or inducer half-life (whichever is longer), before the first dose of study drug. However, if a patient has a strong indication for fungal prophylaxis, then the moderate CYP3A inhibitors fluconazole or isovuconazole (mold-active) is recommended for prophylaxis, and the TAK-659 dose should be reduced to 60mg, along with increased scrutiny for toxicity. Similarly, if the patient develops a fungal infection during a productive intervention with TAK-659/Ixazomib combination, isovuconazole (mold-active) should be used, along with increased scrutiny for toxicity. In general, the use of these agents is not recommended during the study except in cases where such an AE must be managed, and the intermittent schedule of TAK-659/Ixazomib combination will not prevent profound neutropenia. See Section 5.7.2 and the Documents/Info tab of the EDC for

a non-exhaustive list of strong CYP3A mechanism-based inhibitors or strong CYP3A inducers and/or P-gp inducers based on the FDA Draft DDI Guidance.

- c) Grapefruit-containing food or beverages within 5 days before the first dose of study drug.
- 16. Lack of suitable venous access for the study-required blood sampling.
- 17. Diagnosed or treated for another malignancy within 2 years before study enrollment or previously diagnosed with another malignancy and have any evidence of residual disease. Patients with nonmelanoma skin cancer or carcinoma *in situ* of any type are not excluded if they have undergone complete resection.
- 18. Patient has \geq Grade 3 peripheral neuropathy, or Grade 2 with pain on clinical examination during the screening period.
- 19. Known allergy to any of the study medications, their analogues, or excipients in the various formulations of any agent.

4. SUBJECT REGISTRATION

All subjects must be registered through Big Ten Cancer Research Consortium (Big Ten CRC) Administrative Headquarters' (AHQ) electronic data capture (EDC) system.

Subjects must be registered prior to starting protocol therapy. Subjects should begin therapy within 5 business days of registration. However, beginning therapy outside that timeframe will not be considered a deviation.

5. TREATMENT PLAN

This study is an open-label, multicenter, phase I dose escalation and phase IIa study of TAK-659 in combination with Ixazomib, in adult patients with relapsed or refractory AML. This study will include a phase I portion for evaluating the safety of the TAK-659 and Ixazomib, along with monitoring for early efficacy signal, and a single-arm phase II portion. It is expected that up to 18 patients will be enrolled in the phase I portion and up to 36 patients will be enrolled in the phase II portion of this study.

Once enrolled, patients will be given TAK-659 tablets and Ixazomib capsules, once daily for fifteen days (TAK-659) and once weekly (Ixazomib) on days 1, 8, 15, respectively. The cycle length will be 15 days of treatment out of 21 days (one week rest).

To determine the MTD of the combination, a 3+3 approach to dose escalation design will be used. Prior to commencing dose/schedule advance, patients in the immediately preceding cohort will have completed two full cycles of the regimen and will have been evaluated for toxicity. Next, Ixazomib dose escalation will be undertaken (in context of the 15-day treatment cycle/21-day complete cycle including 1 week rest schedule).

At least 6 patients will be evaluated at RP2D (either at MTD or at lower doses as determined) before making a decision to advance to the phase 2 study. In the process of determining or refining RP2D, expansion of more than 1 dose level to at least 6 additional patients is permissible so that pharmacodynamic measures and early signs of clinical activity can be assessed to assist dose selection.

AEs will be assessed, and laboratory values, vital signs, and ECGs will be obtained to evaluate the safety and tolerability of the combination. Toxicity will be evaluated according to NCI Common Terminology Criteria for Adverse Events (NCI CTCAE), version 5. Dose-limiting toxicities (DLTs) are defined in Section 5.5.

Patients will be treated until either disease progression or occurrence of unacceptable study drug-related toxicities. Patients may discontinue therapy at any time. Patients will attend the safety follow up visit 30 days (+10 days) after receiving their last dose of study drug or before the start of subsequent anticancer therapy (other than hydroxyurea) if that occurs sooner.

Assessment of disease response will follow the criteria outlined in the Revised Recommendations of the International Working Group (IWG) for Diagnosis, Standardization of Response Criteria, Treatment Outcomes, and Reporting Standards for Therapeutic Trials in Acute Myeloid Leukemia.

Pharmacodynamic activity of the combination regimen will be assessed in Phase I and Phase II by evaluating bone marrow AML blasts at the time-points specified in the study calendar. Bone marrow biopsies and aspirates for disease response monitoring will be obtained as described in the study calendar. Residual and/or designate samples from bone marrow biopsies and aspirates collected for disease assessment will also be used for analysis of biomarkers as specified in the study calendar.

5.1 Number of Patients

For the phase I portion, up to 18 patients will be enrolled in this study from approximately 2 to 4 study centers in the US. For the phase II portion, 36 patients will be enrolled from these centers.

Patients who are withdrawn from treatment during Cycle 1 for reasons other than toxicity during the phase I portion of the study will be replaced. Patients in the phase II portion of the study, beyond the Simon's two-stage threshold, who are not evaluable for response will be replaced; however, patients who receive at least 1 dose of study drugs, and have measurable disease on bone marrow exam or by biopsy-documented extramedullary tumor at baseline, will be used for futility analyses, including the Simon's two-stage response evaluation.

Duration of Study

Patients, including those who achieve a CR, may receive the combination until they experience disease progression. Patients will discontinue treatment if they have an unacceptable drug-related toxicity. The maximum duration of treatment, however, will be 12 months from Cycle 1 Day 1 (C1D1) unless it is determined that a patient would derive benefit from continued therapy beyond 12 months.

Patients will be followed for 30 days after the last dose of the combination, or to the start of subsequent anticancer therapy, whichever occurs first, to permit the detection of any delayed treatment-related AEs. All patients, including those patients no longer on treatment, will be assessed for survival. Patients who discontinue the study, regardless of reasons for discontinuation, will be followed for up to 12 months after discontinuation of the study drug for survival (every month until death), loss to follow-up, or withdrawal of consent for further follow-up. In addition, information on any subsequent anticancer therapies will be collected during the survival follow-up period. For patients who achieve CR but discontinue study treatment while still in remission, disease progression based upon available local data will also be collected during the survival follow-up period.

The final analyses for the clinical study report may be conducted after all patients enrolled in the study have had the opportunity to complete 3-4 cycles of combination therapy (while still not progressing).

It is anticipated that this study will last for approximately 24-32 months, including 9 to 12 months in the phase I portion, and 15 to 20 months in the phase II portion.

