5.3 Dose Escalation Rules and MTD Definition

Dose escalation will be determined based on the number of toxicities as noted by the algorithm noted in the following Figure 5-1.

Figure 5-1 Dose/Schedule Escalation Algorithm TAK-659 and

TAK-659/Ixazomib Clinical Study Protocol

If 2 or more patients in any dose level experience DLT, enrollment at that dose level will stop. Following consultation between the sponsor and investigators, either the previous dose level will be considered the MTD (if 6 or more patients have been studied at that dose level), the previous dose level will be expanded (if fewer than 6 patients have been studied at that dose level), or a dose level intermediate between the current and the previous dose level will be evaluated.

To define the Maximum Tolerated Dose (MTD), subjects will be evaluated for DLT following two cycles (56 days) of treatment. Decisions to move to next dose escalation cohort will not be made until all subjects complete 2 cycles of therapy at a given dose.

The MTD is defined as the dose level at which fewer than 33% of subjects experience a dose limiting toxicity (DLT), and specifically is the dose level at which less than 2 out of 6 subjects experience DLT. The minimal safe and effective dosing with pharmacodynamic and pharmacokinetic parameters pointing toward the goal of efficacy optimization, will be the recommended dose (RP2D) for the Phase II component of the study. To achieve this, the developing results of safety, tolerability, efficacy, PK and PD in each dose-escalation cohort will be reviewed in real time after each cohort, to determine whether maximal safety and evolving efficacy milestones will have been reached based on examination of two consecutive cohorts, when safety and tolerability measures are within criteria for each.

- The criterion for safety will be DLT <20% within the cohort.
- The criterion for tolerability will be the administration of >80% of expected dose within the cohort.
- The criterion for efficacy will be the dose with an estimation of greater or equal to 25% ORR in the Flt3 mutant cohort, or greater than or equal to 10% ORR in the Flt3 wild-type cohort.
- The criterion for optimizing PK will be: on day 1, equal or greater than 100ng/ml peak (Cmax) TAK-659, or its trough equal or greater than 15ng/ml; on day 15, peak at least 200ng/ml, trough at least 40ng/ml. On the other hand, the day 15 peak should be less than 400ng/ml, and trough should be less than or equal to 100ng/ml.

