8.7 Long Term Follow-up Evaluations

All patients, including those patients no longer on treatment, will be assessed for survival. Patients who discontinue the study, regardless of reasons for discontinuation, will be followed for survival every month for up to 12 months after discontinuation of the study drug or until death, loss to follow-up, or withdrawal of consent for further follow-up, whichever comes first. In addition, information on any subsequent anticancer therapies will be collected during the survival follow-period. For patients who achieve CR but discontinue study treatment while still in remission, disease progression data will also be collected during the survival follow-up period.

Follow up may be accomplished via clinic visit, phone call, or other avenues as appropriate.

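### The final analysis may be cut 63-84 days after the last patient starts, and nothing ties it to the 6-month mortality endpoint or to a minimum follow-up for duration of response

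*Combined protocol and SAP*

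**What the plan says.** **When the analysis may be done.** Section 5.1, under Duration of Study, allows the final study-report analyses to go ahead once all patients "have had the opportunity to complete 3-4 cycles of combination therapy". This is a permission with an earliest date. The plan gives no other data cut-off for the study report.

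**Cycle length.** Section 5: "The cycle length will be 15 days of treatment out of 21 days (one week rest"). Section 5.3 implies 28-day cycles instead: "subjects will be evaluated for DLT following two cycles (56 days) of treatment".

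**Endpoints.** Section 2.2.2 lists DOR, TTP, OS and "Mortality rate at 3 and 6 months" as secondary endpoints. Sections 13.1 and 13.7.2 analyse time-to-event data by Kaplan-Meier with 95% confidence intervals, by FLT3 cohort, and Section 13.7.2 adds a combined cohort for OS. Section 13.2 says that DOR, TTP, bridging to transplant and mortality will also be weighed in deciding whether to expand the study.

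**Follow-up.** Section 8.7: patients who discontinue "will be followed for survival every month for up to 12 months after discontinuation of the study drug". For progression after stopping treatment, Sections 5.1 and 8.7 specify collection only for patients who reached CR and stopped while still in remission.

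**Timeline.** Section 5.1 gives 24-32 months as the length of the study. The synopsis gives 24-32 months as the enrollment period and 48 months as the study duration.

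**The concern.** A 6-month mortality estimate is only as mature as the follow-up behind it. If the report is cut 2 to 3 months after the last patient starts, the most recent patients cannot have been observed to 6 months, and their responses will have had little time to end.

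The cohorts hold at most 16 and 20 patients, so a few early-censored patients widen the intervals noticeably. These endpoints also feed a decision, since the plan brings them into the choice to expand. Most of the survival information will be collected in any case. The earliest analysis date simply does not wait for it.

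**Working it through.** **Inputs.** Cycle length 21 days (Section 5), with 28 days tried as a variant because of Section 5.3. Trigger: 3 or 4 cycles (Section 5.1). Phase II size 36 = 16 + 20 and accrual 15-20 months (synopsis). OS origin: "OS defined as the time from the date of study entry to death" (Section 2.2.2), with study entry not further defined. Section 4: "Subjects should begin therapy within 5 business days of registration", so a 7-day lag was also tried. One month = 365.25/12 = 30.44 days, so 3 months = 91.3 days and 6 months = 182.6 days.

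**Step 1: the plan's own figure.** Phase I plus Phase II: 9 + 15 = 24 and 12 + 20 = 32 months. This reproduces the stated 24-32 months. The synopsis assigns that total to enrollment, which under a 48-month study leaves 48 - 32 = 16 to 48 - 24 = 24 months after accrual. Section 5.1 assigns the same total to the whole study, which would leave no follow-up time after accrual.

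**Step 2: earliest cut.** 3 × 21 = 63 days; 4 × 21 = 84 days.

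**Step 3: shortfall for the last patient** = landmark - (cycles × cycle length + lag).

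| Cycle length | Cycles | Lag (days) | Days from entry at cut | Short of 3 months | Short of 6 months |
|---|---|---|---|---|---|
| 21 | 3 | 0 | 63 | 28.3 | 119.6 |
| 21 | 4 | 0 | 84 | 7.3 | 98.6 |
| 21 | 3 | 7 | 70 | 21.3 | 112.6 |
| 21 | 4 | 7 | 91 | 0.3 | 91.6 |
| 28 | 3 | 0 | 84 | 7.3 | 98.6 |
| 28 | 4 | 0 | 112 | passed by 20.7 | 70.6 |
| 28 | 3 | 7 | 91 | 0.3 | 91.6 |
| 28 | 4 | 7 | 119 | passed by 27.7 | 63.6 |

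The 6-month landmark is missed in every variant, by 64-120 days. The 3-month shortfall shrinks to days or disappears.

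**Step 4: number of Phase II patients without potential follow-up to the landmark**, assuming uniform accrual: 36 × (landmark in months - cut in months) / accrual in months. The cuts are 63/30.44 = 2.07 and 84/30.44 = 2.76 months.

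| Cut (days) | Accrual (months) | Short of 6 months | Short of 3 months |
|---|---|---|---|
| 63 | 15 | 36 × (6 - 2.07)/15 = 9.4 (26.2%) | 2.2 |
| 63 | 20 | 7.1 (19.7%) | 1.7 |
| 84 | 15 | 7.8 (21.6%) | 0.6 |
| 84 | 20 | 36 × (6 - 2.76)/20 = 5.8 (16.2%) | 0.4 |

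These counts include anyone who has already died by the cut. Such patients contribute fully to the estimate, so for a given accrual assumption 6-9 is an upper limit on the number censored before 6 months for this reason.

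**Step 5: DOR.** Section 8.3 grades Phase II best response on the Cycle 3 Day 22 marrow, which is study day 42 + 22 = 64. For the last-enrolled patient, a cut at day 63 leaves no DOR follow-up and a cut at day 84 leaves 84 - 64 = 20 days. A response first documented on Cycle 1 Day 15 would have 63 - 15 = 48 to 84 - 15 = 69 days.

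**Step 6: what a 6-month cut adds.** 182.6 - 84 = 98.6 to 182.6 - 63 = 119.6 days, or about 3-4 months. That fits within the 16-24 months left under the synopsis timeline.

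**The case against.** The strongest reply is that Section 5.1 only permits an early analysis. A sponsor that waits complies fully, and other text suggests that mature results are intended: the 48-month duration in the synopsis, the definition of patient completion in Section 6.5 (built on death, the 12-month follow-up window, or at least a year on treatment), and the requirement in Section 14.6 to post all primary and secondary results within a year of completion. This stands as far as intent goes. None of it fixes the date of the study report, so a report cut at 63 days would also comply.

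Second, Kaplan-Meier is prespecified, and Section 13.1 reports the percentage censored. This also stands. Late patients stay in the risk set until the cut and their deaths count. A reader might infer that the estimates would be biased or that these patients are thrown away. The documents support neither; what is lost is precision in descriptive estimates that carry no hypothesis test.

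A reader might also infer that 3-month mortality is compromised in the same way. It is not: the gap at 4 cycles is 7 days and can vanish, depending on how study entry and cycle length are read.

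Finally, it is tempting to say that waiting makes every secondary endpoint mature at no cost. That holds for survival. For patients with CRp, CRi or PR who stop without progression, for example to go to transplant, no later collection of progression is specified, so a later cut alone would not complete their DOR or TTP.

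**Conclusion.** The point holds as a cheap improvement. The plan sets an earliest date for the final analyses that suits the response rate but not 6-month mortality, OS, DOR or TTP, and sets no later date for those. The 6-month shortfall for the last patients is robust to every reading of cycle length and entry date tried.

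The count of affected patients assumes full enrollment of 36, uniform accrual over 15-20 months and a cut at the earliest permitted date. Accrual concentrated late would raise it, and a later cut would lower it. The 0-20 days of DOR follow-up is the worst case; earlier responders and earlier enrollees have more.

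The primary response-rate analysis is not touched. Nor do the documents support the reading that the plan requires an immature report: it allows one.

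**What to change.** - In Section 5.1, keep 3-4 cycles of opportunity as the trigger for the response-rate read-out.
- In Sections 5.1 and 13.7.2, state that the final analysis of 6-month mortality, OS, DOR and TTP takes place no earlier than 6 months after the last Phase II patient's first dose. Registration precedes first dose (Section 4), so this also covers 6 months if study entry means registration.
- Reconcile the 24-32 month study duration in Section 5.1 with the 24-32 month enrollment period and 48-month duration in the synopsis. The two-cycle length in Section 5.3 and the 21-day cycle in Section 5 also need reconciling, since the trigger is counted in cycles.

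**Cost.** Wording changes only, with no added patients, and no added survival contacts because monthly survival follow-up is already planned for up to 12 months after stopping drug. The secondary tables come about 3-4 months later. The benefit is full for survival and partial for DOR and TTP, because progression after stopping treatment is specified only for patients who stop in CR.
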